10. SETTING

The location where the research team will conduct the research will be at MCHH's community center ([name]). The space has been previously used by MCHH to conduct larger workshops

in-person and can accommodate any necessary physical spacing needed for respiratory infection control. In addition, the community space has two private rooms to accommodate needs for participant privacy.

11. STUDY INTERVENTION

This randomized controlled trial will be done in partnership with MCHH. Previous partnership with MCHH and UW-Madison researchers developed cervical cancer educational workshops designed by CHWs to provide innovative mixed-modality education consisting of pictographs, flipcharts, videos, and hands-on models. These workshops to be conducted in Hmong, Karen, and Burmese and Karen languages were tested in mock workshops with Hmong and Karen participants and through a community advisory panel prior to dissemination. This approach caters to the unique culture and communication styles of Southeast Asian immigrant and refugee populations.

All workshops will be conducted by the CHWs on the study team. If the CHW is not fluent in the target language (such as Karen or Burmese), then the CHW will conduct all study activities in English with a translator available to translate all activities.

All participants attending a workshop will be randomized as a group to either a control or intervention group. Workshops in the control group will provide education recommending standard of care (clinician-collected hrHPV testing and cytology screening). Workshops in the intervention group will be offered the same education with additional education on the option of self-collection (HPV testing only) for their screening method. All participants will have the same basic demographic information collected in MCHH's standard intake form with an additional question on current barriers to screening.

Participants will self-select which workshop day they would like to attend depending on their preferred language. Participants can attend any available date a workshop is being offered until filled. Participants will be blinded to knowing which workshops are control or intervention groups. Participants during consent will be made aware there are two different groups and the difference between the intervention and control group is the education provided and screening method offered at the end of the education session. Participants will be provided the full study details at the end of their participation.

We anticipate a total of thirty workshops, fifteen of which will be control and fifteen of which will be intervention, will be planned in total over a sixteen-month period (Table 1). All workshops will have 8 participants recruited due to limited space of the community center, time, and to accommodate physical spacing needs. There will be two workshop sessions per day (one in the morning and one in the afternoon).

Table 1. Planned Number of Hmong and Karen Participants in the Intervention and Control Workshops

Intervention Workshop	1	2	3	4	5	Total
Hmong	8	8	8	8	8	40
Karen	8	8	8	8		36
Karen	8	8	8			24
Burmese	8	8	8			24
Control Workshop						
Hmong	8	8	8	8	8	40
Karen	8	8	8	8		36
Karen	8	8	8			24
Burmese	8	8	8			24

[figure not shown]
After workshop conclusion, participants will be offered same-day on-site cervical cancer screening depending on assignment in the control or intervention group (clinician-collected screening or self-collection screening, respectively). Participants, regardless of engagement in screening, will then complete a post-evaluation workshop survey (consisting of two surveys, see Appendix C).

Due to ethical concerns and our hypothesis that this population is less likely to do cervical cancer screening if offered clinician-collected screening only. Participants in the control workshops who answer “yes” on the survey to the question “If given the option, instead of having a clinician collect the sample, would you want to collect the sample on your own?,” will be subsequently offered self-collection for their screening method. CHWs will provide to these participants a 5-minute 1-on-1 instruction tutorial on self-collection, translated handout, private room to collect a sample, and then samples sent to the laboratory per protocol.

Similarly, participants will be made aware during the education of the self-collection method, that this is not a usual method that is offered in many clinical practices. If a participant were to visit their usual primary care doctor for an exam, a pelvic examination to obtain a clinician-collected cervical swab for HPV testing and pap smear is the usual method which they should anticipate. We are offering self-collection as studies show growing validity of HPV self-sampling, particularly among hard-to-reach populations.¹⁴⁻¹⁸ With this understanding, self-collection will be offered and encouraged although if participants desire clinician-collection instead this is option will also be made available.

The final part of the study is to fully explain the purpose of the study to each participant, including why subjects could not be informed of all study procedures prior to, and during the study up to that point. The study procedures in question were providing standard-of-care education on cervical cancer screening to both groups and additional information on self-collection for HPV screening to the intervention group. The education on the option for self-collection is withheld from the control group. This information could not be disclosed to the study participants prior to the end of the study to effectively measure participation rates for self-swab if they are provided the education or education is withheld.

Full workflow of design for participation in workshops and post-workshop screening is outlined in Figure 1.

Figure 1. Participant Engagement Workflow

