8. CONSENT PROCESS

The informed consent process will make clear that participation in any and all aspects of the study are voluntary, and that participants may end their participation at any time.

The informed consent process will be conducted following all federal and institutional regulations relating to informed consent. Informed consent will be obtained at the beginning of participation through the following process:

- A link to a pre-record video will be provided to each participant at the time of recruitment. This video will be created prior to the start of the study which CHWs employed through MCHH will provide consent information using the pre-approved oral script.
 - o If the CHW does not speak the spoken language, then the CHW would follow the script in English and a translator would then translate the information to the participant language.
- Upon arrival to the study, participants will be asked if they have seen the pre-recorded video:
 - o If any participant reports the video was not viewed – it will be shown to all participants.
 - o CHW provides a summary about the study, study activity, and consent items, then answering any questions which may arise.

- If the CHW does not speak the spoken language, then an the CHW would provide the information in English and a translator would then translate the information to the participant language. Questions or comments will also be translated back to the CHW to be answered. The translator will serve as witness to ensure that study materials and consent were understood by the participant.
- It will be noted in a participant's study record noting they provided verbal consent.

Participants will be informed of random assignment into two groups: standard-of-care control group and intervention group. Due to the nature of this study, we will not disclose which group the participant belongs to although will provide a debrief session at the end of the study about what information could not be given at the time of consenting, and why they could not be told at that time.

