Participants will not be told the full procedures prior to enrollment due to the need to test the hypothesis in this study. Participants in the control group are initially only provided educational materials about the standard of care for cervical cancer screening. While self-collection may or may not be known by the workshop participants in the control group, this is not standard of practice nor usually recommended by clinicians. Whereas the intervention group is provided additional materials about self-collection in the core educational material and is offered as a screening option immediately at the end of the workshop. The uptake of cervical cancer screening by workshop participants at the end of the workshop will then be compared between these two groups to determine.

The informed consent process will include contact information for the PI, who can be contacted if participants or potential participants have questions or concerns.. Informed consent forms will be available in written English, Hmong, or Karen for reference only. All participants will have access to the pre-recorded video in their native language for reference.

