9. PROCESS TO DOCUMENT CONSENT IN WRITING

This study requests of waiver of written documentation of consent

- A written script of the information will be provided orally.
- Pre-recorded video of oral script will be available to all participants for future reference.
- Research presents no more than minimal risk of harm to subjects.
- The research involves no procedures for which written consent is normally required outside of the research context.

This consent requests an alteration of the consent process (HRP-410) due to the following criteria:

- The study involves no more than Minimal Risk to the participants based on clinical standard of care.
- The study could not be practically carried out without the alteration. Participants will be blinded to which group they are randomized in order measure participation rates based on which type of screening method they are offered (clinician-collection vs self-collection)
- The alteration will not adversely affect the rights and welfare of the subjects. Participants will be provided the risks of each collection method in detail during the workshops. If a participant declines the type of screening they are offered will then be offered the other screening method.
- Subjects will be provided the additional pertinent information after participation.
- High proportion of participants in this study population have no or low reading or writing literacy in English or the native language.

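### The protocol contradicts itself on what control women learn about self-collection before the first screening offer, and the undefined uptake endpoint leaves the direction of any resulting bias open

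*Combined protocol and SAP*

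**What the plan says.** **Withholding.** Section 8 states: "Participants in the control group are initially only provided educational materials about the standard of care for cervical cancer screening". It also says that "we will not disclose which group the participant belongs to", and that "Participants will not be told the full procedures prior to enrollment due to the need to test the hypothesis in this study". Section 11, describing the debrief, states: "The education on the option for self-collection is withheld from the control group". Section 13.1.2 limits control education to clinician collection. In Appendix C, both control branches of the survey (Sections B and C) tell the woman that self-collection was not discussed in her workshop.

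**Disclosing.** Section 11 says women are made aware during consent that "the difference between the intervention and control group is the education provided and screening method offered at the end of the education session". Section 9, in the grounds for altering consent, states: "Participants will be provided the risks of each collection method in detail during the workshops". The next sentence of Section 9 adds: "If a participant declines the type of screening they are offered will then be offered the other screening method".

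**Second offer.** Section 11 places it after the survey. Control women who answer yes to wanting to collect their own sample "will be subsequently offered self-collection for their screening method".

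**Endpoint.** Section 8 speaks of comparing uptake at the end of the workshop. Section 20.3.1 counts women who engage through services offered after the workshop, or who report a desire to follow up with their own provider. It does not limit uptake to the first or assigned offer.

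**The concern.** The protocol itself says that disclosing self-collection early would defeat the measurement. Yet staff running a control workshop have one instruction to describe the risks of each method and another to leave self-collection out. If the risks are given, a control woman knows before the first offer that a less invasive method exists, and she may decline in the hope of getting it.

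The incentive differs between arms. In the control branch of Appendix C, a woman who accepts clinician collection reaches the end of the survey with no self-collection step, and the one-to-one instruction appears only in the branch for unscreened women. Intervention women may have clinician collection instead if they want it (end of Section 11), so they have no matching reason to wait. What is at stake is the primary contrast, and a script already delivered cannot be taken back.

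**Working it through.** **1. The passages side by side**

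| Question | Withheld from control | Disclosed |
|---|---|---|
| Is self-collection covered in the control workshop? | No: Sections 8, 11 (debrief), 13.1.2; Appendix C | Yes, read literally: Section 9 (risks of each method) |
| Do women know the method offered differs by group? | Section 8: full procedures not told before enrolment | Section 11: told during consent |
| Do women know a decliner gets another offer? | No passage says they are told before the first offer | Section 9 commits to the offer, as a ground for the alteration |

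The first row is a direct conflict. The second is a tension: a difference in method is disclosed, but self-collection is not said to be named. The third is not a documented disclosure.

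**2. The plan's own figure.** Section 20.2 gives power 0.85 for 0.81 against 0.93 with 125 per arm at one-sided 0.05. The exact one-sided Fisher test gives 0.854, and all nine detectable rates in the table are reproduced. The same test is used below, with women treated as independent, as the plan does.

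**3. If only the first offer counts.** Inputs:
- n = 15 workshops × 8 = 120 per arm (Section 11).
- Base rate p = 0.71, the middle value in Section 20.2, with no true difference between arms.
- h = share of would-be control acceptors who wait. This is assumed; the documents give none.

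Counted control uptake = p(1 − h), against 0.71 in the intervention arm.

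| h | Control uptake | Chance of a false positive |
|---|---|---|
| 0 | 0.71 | 0.037 |
| 5% | 0.71 × 0.95 = 0.67 | 0.119 |
| 10% | 0.71 × 0.90 = 0.64 | 0.273 |

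At h = 10% the chance is 0.209 with a base rate of 0.61 and 0.380 with 0.81. With 125 per arm and a base rate of 0.71, the 5% and 10% figures are 0.122 and 0.281.

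**4. If later screening also counts.** Let r be the share of waiters later counted as screened. Control uptake = p[1 − h(1 − r)]. With p = 0.71, n = 120 and h = 10%:
- r = 0.5: 0.71 × 0.95 = 0.67, false-positive chance 0.119.
- r = 1: 0.71, false-positive chance 0.037, so there is no distortion.

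**5. If genuine decliners also cross over and are counted.** Take a true contrast of 0.71 against 0.85 with 125 per arm. If half the gap is counted as control uptake, control becomes 0.71 + 0.5 × 0.14 = 0.78. Power falls from 0.820 to 0.356. The distortion now runs toward no difference.

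**The case against.** The strongest reply is that the operational text already protects the contrast. Section 11 orders the steps as first offer, survey, then self-collection. Appendix C asks whether clinician collection took place before it raises self-collection, and its wording shows that control workshops are meant to omit the topic. On that view, Section 9's sentence is loose drafting, meaning that each workshop covers its own method. This is a reasonable reading of intent, and it means the conflict may never surface at the site. But Section 9 has no such limit and supports the consent request, so it should say what is meant.

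A reader might go further and infer that control women will be told they can hold out for the other method, so that control uptake is biased down. The documents do not support this. The commitment to decliners is a justification for altering consent, and nowhere is it said to be told to women before they answer. The consent script is known here only from the protocol's description. Downward bias also requires that only first-offer acceptance counts, and Section 20.3.1 can be read otherwise.

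Nor is the problem wholly beyond the analysis. Section 16.2 stores the type of screening done, so control uptake could be reported with and without self-collected samples. That would show how far waiting could matter, but it could not separate women who waited from women who would have declined anyway.

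**Conclusion.** The contradiction over what control women learn before the first offer is established from the text. That it would contaminate the primary contrast if Section 9 were followed literally rests on the protocol's own reason for withholding. A bias of known direction or size is not established.

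Under a first-offer endpoint, small shares of waiting matter: with none of the waiters counted, 5% to 10% waiting moves the false-positive chance from about 0.04 to between 0.12 and 0.27. Under the broader wording of Section 20.3.1 the effect shrinks to nothing, or reverses into dilution. These figures assume independent women, equal true acceptance in the two arms (except in the dilution example) and waiting shares that have no source in the documents. The power table in Section 20.2 is not affected.

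**What to change.** 1. Reword Section 9 so that each workshop covers only the risks of the methods taught in that arm. In control, give self-collection risks in the existing one-to-one tutorial, before any self-sample.
2. State that no second offer is mentioned until the response to the first has been recorded. Record that response in the REDCap study record, because Section 16.2 keeps the survey anonymous and unlinked to the study ID.
3. Define primary uptake in Section 20.3.1 as acceptance of the first, assigned offer. Report second-offer screening and stated desire to follow up separately. Say how an intervention woman who asks for clinician collection is classified.
4. Reconcile Section 11's consent description with Section 8 and the debrief text, so that wording before the first offer does not signal an alternative method.
5. Reconcile who receives the second offer: Section 9 says any decliner, while Section 11 says control women who answer yes on the survey.

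The cost is redrafting plus an IRB amendment, and slightly less disclosure before the first offer. Item 4 is for the IRB to decide. Section 9 argues for blinding women to their group, which does not clearly extend to leaving out that the methods differ.

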13.1.4 Post-Workshop Sample Collection

Immediately after workshops, participants will be offered same-day opportunity to engage in cervical cancer screening either through clinician collection (if in the control) or self-collection (if in the intervention group). Participants who do not desire screening through the program will be encouraged to attend cervical cancer screening with their local health department or provider.

Pregnant women will be excluded from this study if they are known to be pregnant at the time of screening, although additional measures will be taken prior to sample collection for women unaware of pregnancy status. All participants will be asked the date of their last menstrual period (LMP). Participants will be requested to provide a urine sample for on-site urine pregnancy testing if more than six weeks from LMP unless post-menopausal or meeting criteria of relative certainty a woman is not pregnant. CDC 2016 Selective Practice Recommendations for reasonable certainty states, a health care provider can be reasonably certain that women is not pregnant if she has no symptoms or signs of pregnancy and meets any one of the following criteria:

- is ≤7 days after the start of normal menses
- has not had sexual intercourse since the start of last normal menses
- has been correctly and consistently using a reliable method of contraception
- is ≤7 days after spontaneous or induced abortion
- is within 4 weeks postpartum
- is fully or nearly fully breastfeeding (exclusively breastfeeding or the vast majority [≥85%] of feeds are breastfeeds), amenorrheic, and <6 months postpartum¹⁴

Results of the urine pregnancy test will be provided immediately to the participant and if positive, excluded from the remaining of the study although still counted as a participant. Due the possibility that participants who are pregnant and included in the study (educational workshops only, will not be included in either screening method—clinician-collected or self-collection). For risks involved with the educational workshop portion of the study:

- The research involves no more than minimal risk to pregnant women and fetuses.
- The research holds prospect of direct benefit to the pregnant women, the prospect of direct benefit both to the pregnant woman and the fetus, or no prospect of benefit for the woman nor the fetus.

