18. SHARING OF RESULTS

Each participant who undergoes cervical cancer screening after the workshop, either through clinician collection (if in the control) or self-collection (if in the intervention group), will be contacted by a CHW or other staff member of MCHH, and the participant's results will be given to her. Recommendations will be for all women to present in-person although if declines, results will be given via telephone. All results will also be mailed to the participant and preferred primary care provider (if applicable).

Dissemination of findings in this study will be made available in a journal that is yet to be determined although will be funded through the sponsor agency and in an open access journal. Authorship plans will include at minimum, Drs. [name], [name], [name], and [name] as authors, order of authorship to be determined. Subject's identity will remain confidential on presentation of data or publication.

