20.2 Sample Size Justification

For this pilot study, we will enroll 250 participants, which is based on the feasibility of the number of workshops possible during the program length, funding, and resources available through MCHH.⁹ Power estimates are based on comparing the rate of participation between the intervention arm (participants offered self-collected hrHPV) and the control arm (participants offered clinician-collected screening). Estimates of screening rates for the Hmong women population (percent that have had a clinician-collected screening in the last 2-3 years) range from 61- 81%. As we do not have estimates for rates for Karen, Karen, Burmese, or Hmong women, we will use these estimates for participation rates in the control arm. The table below shows the detectable participation rates (and differences between proportions) for the intervention arm for different combinations of power (1- β) and values for the control arm from 0.61-0.81, for the hypotheses $H_0: P \leq p_0$ vs. $H_1: P > p_0$, where p_0 is the rate of participation in the control arm, for a sample size of 250 (125/arm), with a one-sided level 0.05 binomial test.

Control Participation Rate	Detectable Participation Rate (Difference)		
	0.80	0.85	0.90
0.61	0.77 (0.16)	0.78 (0.17)	0.79 (0.18)
0.71	0.85 (0.14)	0.86 (0.15)	0.87 (0.16)
0.81	0.93 (0.12)	0.93 (0.12)	0.94 (0.13)

As an example, if there is a participation rate of 0.81 for those offered clinician-collected screening, we will be able to detect a rate of 0.93 (a difference of 0.12) in the participants offered self-collected hrHPV with a one-sided level 0.05 binomial test with a power of 0.85.

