20.3 Statistical Methods

20.3.1 Primary Outcome Measures and Analysis:

The primary outcome measure is uptake of cervical cancer screening. The results will be reported through summary statistics of the number of participants in each group subsequently engaging or seeking out cervical cancer screening either through services offered after workshop education or self-reported desire to follow up through their community health care provider. Comparisons between the study arms will be based on a binomial test. The analysis will indicate if participants offered additional self-collection education would be more willing to engage in cervical cancer screening. Summary statistics will also include uptake of screening differentiated by reported ethnicity.

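### Section 20.3.1 sets no first-offer limit on primary uptake, so read literally it counts control women who self-collect at the second offer as control uptake

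*Combined protocol and SAP*

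**What the plan says.** Section 20.3.1 is the only text that says how the primary outcome is counted. It counts participants in each group who engage in or seek out screening "either through services offered after workshop education or self-reported desire to follow up through their community health care provider". It names no method, order of offer or cut-off point. It then gives the purpose: to learn whether women offered the extra self-collection education are more willing to be screened.

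Section 11 sets out a sequence: an on-site offer that depends on arm, then the survey, then a further step for control women. Those who answer yes to a question about collecting their own sample "will be subsequently offered self-collection for their screening method", with a short individual tutorial, a private room and laboratory processing. Section C of the Appendix C survey has a response for a control woman who was not screened at first and then gives a self-sample.

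Section 9 describes the second offer more broadly, for either arm: "If a participant declines the type of screening they are offered will then be offered the other screening method".

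Other passages describe the comparison by what was offered or taught. Section 9 says the aim is to "measure participation rates based on which type of screening method they are offered". Section 11 says information was withheld "to effectively measure participation rates for self-swab if they are provided the education or education is withheld". Section 20.2 says: "Power estimates are based on comparing the rate of participation between the intervention arm (participants offered self-collected hrHPV) and the control arm", the latter being women offered clinician-collected screening. Section 13.1.4 describes the post-workshop offer as clinician collection in control and self-collection in intervention.

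**The concern.** A self-sample given at the second offer is a service offered after the workshop education, so the counting sentence taken at its word includes it as control uptake. By then the control woman has been taught self-collection and given the device, which is what distinguishes the intervention arm. Counting her as a control success credits the control arm with the effect under test.

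This crossover is foreseeable. Section 11 explains that the second offer exists because women are expected to screen less when only clinician collection is offered. Unless the rule is written down, an analyst following Section 20.3.1 literally would report a diluted difference, while one following the purpose sentence would report a different numerator from the same data.

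**Working it through.** **Reproducing the plan's figure.** Inputs from Section 20.2: 125 women per arm, one-sided level 0.05, control rates 0.61/0.71/0.81, and detectable intervention rates 0.77/0.85/0.93 in the 0.80-power column. The exact power of a one-sided Fisher test, summed over both binomial distributions, is 0.837/0.820/0.854. The last value matches the worked example (0.81 against 0.93, stated power 0.85). Rounded up to the next 0.01, the Fisher detectable rates match all nine cells of the table. A one-sample binomial test against a fixed control rate would give power of at least 0.98, so the table is a two-sample calculation. It takes the control rate from clinician-collected screening alone.

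**Adding the second offer.** Let p0 and p1 be the control and intervention rates, and c the share of control decliners who self-collect at the second offer. The documents do not give c; 10% and 20% are assumed. Stated intent is left aside.

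- Counted control rate = p0 + c(1 − p0)
- Counted difference = (p1 − p0) − c(1 − p0)
- Share of the difference removed = c(1 − p0)/(p1 − p0)

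| | 0.61 vs 0.77 | 0.71 vs 0.85 | 0.81 vs 0.93 |
|---|---|---|---|
| Power, c = 0 | 0.837 | 0.820 | 0.854 |
| Power, c = 10% | 0.635 | 0.654 | 0.742 |
| Control rate, c = 20% | 0.688 | 0.768 | 0.848 |
| Difference, c = 20% | 0.082 | 0.082 | 0.082 |
| Share removed, c = 20% | 0.078/0.16 = 49% | 0.058/0.14 = 41% | 0.038/0.12 = 32% |
| Power, c = 20% | 0.376 | 0.444 | 0.591 |

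At c = 20% the expected number of control women who cross over is 125 × (1 − p0) × 0.20 = 9.75, 7.25 and 4.75.

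**Varying what was held fixed.**

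- Larger true effect (assumed): for 0.61 against 0.85, c = 20% leaves power at 0.90. For 0.71 against 0.93 it leaves 0.97. A larger crossover still hurts: 0.61 against 0.85 at c = 50% gives 0.20.
- Equal acceptance: if 20% of decliners in both arms accept a second offer and all are counted, the intervention rates become p1 + 0.20(1 − p1) = 0.816/0.880/0.944. The differences are 0.128/0.112/0.096 and power is 0.72/0.71/0.75.

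**Can the two kinds of control sample be told apart?** Section 16.2 lists study ID, workshop date and type of screening for REDCap, but neither arm nor session, and Section 11 runs two sessions a day. The Appendix C survey does record workshop type and whether a woman was screened before the second offer. However, Sections 13.1.3.2 and 16.2 say its responses are not linked to study ID.

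**The case against.** The strongest reply is that the intended rule can be inferred. The purpose sentence in Section 20.3.1, together with Sections 8, 9, 11, 13.1.4 and 20.2, leans towards uptake by what was offered or taught. Section 11 already puts the second offer after the survey, and Figure 1 may mark the counting point. This largely stands. A reader might infer that the plan leaves two numerators evenly open; the documents do not support that. What remains is that the one sentence defining the count says otherwise when applied as written, and no readable text excludes the second-offer sample.

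A second reply is that the power figures are close to a worst case. They use the minimum detectable differences, which Section 20.2 does not present as expected effects, and that section bases the pilot's size on feasibility. They also hold intervention uptake fixed, although the Section 9 sentence covers decliners in either arm. This stands too, and the variations above show how much it matters. The figures also ignore randomisation by workshop, so none of them should be read as this trial's actual power.

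A third temptation is to conclude that stated intent must leave the primary outcome. Section 20.3.1 includes intent explicitly. Whether to keep it is a separate endpoint decision that does not follow from this point.

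**Conclusion.** The point holds as a conflict between the counting sentence and the comparison the plan says it is making. Applied literally, Section 20.3.1 includes control second-offer self-samples and biases the primary difference towards zero. That conclusion needs no assumed number.

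Its size depends on a crossover share that the documents do not give. At the smallest detectable differences, 20% crossover among control decliners removes 49%/41%/32% of the difference, and power falls from 0.84/0.82/0.85 to 0.38/0.44/0.59. The assumptions are 125 per arm, a one-sided Fisher test, independent women, no second-offer gain in the intervention arm and intent left aside. With larger effects or equal acceptance in both arms the loss is much smaller.

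It should be fixed before analysis. Confidence is medium, because Figure 1 and the survey's skip logic cannot be read here.

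**What to change.** Leave all offers to participants unchanged.

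1. In Sections 2 and 20.3.1, state that screening collected on site counts towards primary uptake only if collected at the first post-workshop offer, before the survey and any second offer. In the intervention arm this includes clinician collection chosen at that offer, which Section 11 allows.
2. Report control self-samples from the second offer as a separate secondary outcome.
3. Add arm or workshop session to the REDCap record by study ID. Once arm is known, a control self-sample identifies itself as second-offer. An order-of-offer field is needed only if intervention decliners also receive a second offer.
4. Reconcile the wording on who receives a second offer: Section 9 covers any decliner, while Section 11 covers control women who answer yes on the survey. Check the Appendix C skip logic against the reconciled text.

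The cost is a wording change in two sections and one more field for staff to complete (two if order of offer is needed). The downside is that second-offer samples leave the primary count.
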